### 7.3 Test of Cross Over Effect

This is a cross-over study and potential carry-over effect will be assessed. Logistic regression will be used to test carry-over effect by using the regiment sequence as an indicator variable. A P-value of 0.1 or larger will be deemed as supporting the assumption of no carry-over effect. If the carry-over effect is present, further analysis will be performed by adopting appropriate statistical methods (e.g., *Laird, et al. 1992*).

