**Propofol (P) Regimen**

The initial target effect-site concentrations of propofol will be 0.5 µg/ml followed by incremental increases in the target effect-site concentrations of 1.5, 2, 2.5, 3, 4, 6, or 8 µg/ml until MOAA/S scales at values less than 2 is reached. The propofol concentration will be decreased by the same steps until consciousness re-occurs.

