**Propofol with Remifentanil (R) regimen**

Where remifentanil is administered with propofol, approximately 2 minutes before starting propofol, to attain an effect-site targeted concentration of remifentanil of 4 ng/ml, remifentanil will be given by a continuous infusion. Approximately within 7 minutes, the infusion rate of Remifentanil may be adjusted to maintain the effect-site concentration of remifentanil of 4 ng/ml throughout the study.

The initial target effect-site concentrations of propofol will be 0.5 µg/ml followed by incremental increases in the target effect-site concentrations of 1.5, 2, 2.5, 3, 4, 6, or 8 µg/ml until MOAA/S scales at values less than 2 is reached. The propofol concentration will be decreased by the same steps until consciousness re-occurs.

The equilibration time for each targeted plateau will be at least 12 minutes. The BIS value will be recorded, and MOAA/S score will be assessed when the patient is awake and at the different targeted concentrations.

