### 7.2.1 BIS Value Analysis

The volunteers will receive two regimens of anesthesia with different drug combinations, with at least a 1-week washout period between regimens. Once the pre-procedure part completed, the subject will be sequentially assigned to start with either Propofol (P) or Propofol with 4 ng/ml of Remifentanyl (R) regimens, as shown in Figure 1. The volunteers will have BIS Monitoring System, the 4 Channel BISx, and BIS bilateral sensor placed on their forehead during these regimens to study the effects of these drugs on the brain. Each volunteer will be given a dose range of sequences of the target drug to achieve targeted drug concentration

The modified Observer's Assessment of Alertness/Sedation (MOAA/S) scale will be used to perform sedation/ loss of consciousness assessment. Any subject who responds to any verbal command with MOAA/S assessment score of 3, 4, and 5 will be considered as responsive. Subjects with MOAA/S assessment score of 0, 1, and 2 will be considered unresponsive.

The BIS is a variable derived from the electroencephalograph (EEG) that has been reported to have the ability to measure the hypnotic component of the anesthetic state. It is a dimensionless number from 0 to 100, and decreasing values indicate more sedation and hypnosis.

The MOAA/S scales and BIS value will be assessed and recorded when the subject is awake and at different drug concentrations. The relationship between anesthetic agent concentrations and BIS responses will be modeled using the Sigmoid  $E_{max}$  model (Hill equation). The model is shown as follows:

$$E = E_0 + \frac{E_{max} \times C^\gamma}{(C_{50})^\gamma + C^\gamma}$$

In this model, the treatment effect ( $E$ ) is related to the measured concentration ( $C$ ) of an anesthetic agent according to a nonlinear function with  $\gamma$  defining the steepness of the concentration effect relationship.  $E_0$  is the baseline measurement of the responsive endpoint when no drug is present and  $E_{max}$  is the maximum drug effect. The target parameter  $C_{50}$  is the concentration at which 50% subjects are unresponsive.

With zero effect when no drug is applied, the above model can be expressed as a fraction of maximum drug effect, that is,

$$P = \frac{1}{1 + (C_{50}/C)^\gamma}$$

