### Secondary Objective:

To determine BIS95 (BIS value at which 95% of subjects will be unresponsive at given drug concentrations) and other dose-response parameters.

The relationship between anesthetic agent concentrations and BIS responses will be modeled using the Sigmoid model (extended logistic model) as discussed previously.

The dose-response relationship by drug concentration will be presented. The estimated BIS values along with 95% confidence intervals will be provided for propofol with or without remifentanyl regimens.

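### SAP 7.3: if the regimens are pooled, the sequence term tests only unequal carry-over, so a second-session shift common to both would pass as no carry-over at about 20 subjects

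*SAP*

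**What the plan says.** SAP 7.3 sets out the whole carry-over assessment in three steps. The test: "Logistic regression will be used to test carry-over effect by using the regiment sequence as an indicator variable". The decision rule: "A P-value of 0.1 or larger will be deemed as supporting the assumption of no carry-over effect". The consequence: "If the carry-over effect is present, further analysis will be performed by adopting appropriate statistical methods". It does not state the outcome variable, the other model terms, how repeated readings within a subject are handled, or whether the regimens are fitted together or separately. No term for first versus second session appears anywhere in SAP section 7.

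The SAP requires "at least a 1-week washout period between regimens". Its descriptions of the two regimens give the same nominal propofol steps: 0.5 µg/ml, then "incremental increases in the target effect-site concentrations of 1.5, 2, 2.5, 3, 4, 6, or 8 µg/ml". Escalation runs "until MOAA/S scales at values less than 2 is reached". The protocol (10.5.2.4 and 10.5.2.5) also gives both regimens the same steps, and ties the end of escalation to BIS and investigator discretion. The R regimen adds remifentanil at 4 ng/ml.

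Results are reported by regimen. SAP 7.9 says: "The estimated BIS values along with 95% confidence intervals will be provided for propofol with or without remifentanyl regimens". The protocol synopsis (Statistics) likewise says that the data are analysed for each regimen.

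**The concern.** The rule claims to address whether there is any carry-over. In a two-period, two-regimen crossover, a sequence term in a pooled model addresses a narrower question: whether the carry-over left by one regimen differs from that left by the other. Both regimens share nominal propofol steps and the same MOAA/S and stimulation procedure, so some of any effect of a first session on the second could be common to both orders. That common part is what the pooled test cannot see.

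If only the difference between regimens were reported, a common shift would largely cancel there too. Here, however, BIS50 (primary) and BIS95 (secondary) are reported for each regimen, and with balanced orders about half of each regimen's sessions are second sessions. A large p-value would then give reassurance that the test cannot supply.

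**Working it through.** **The plan's own figure.** SAP section 6 gives about 20 subjects, ±15% allowable error on BIS50, CV 25%, alpha 0.05 and power above 80%. A one-sample calculation gives:

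- Two-sided: ((1.960 + 0.842) × 0.25/0.15)² = 21.8, so 22 subjects.
- One-sided: ((1.645 + 0.842) × 0.25/0.15)² = 17.2, so 18 subjects.

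The size of about 20 is reproduced closely enough. It concerns BIS50; the plan states no power for the carry-over test.

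**Algebra, additive model, balanced orders.** Let mP and mR be the first-session means of the regimens and s a plain session effect. Let a be the carry-over from a P session into the following R session, and b the carry-over from an R session into the following P session.

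| Order | First session | Second session |
|---|---|---|
| P then R | mP | mR + s + a |
| R then P | mR | mP + s + b |

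- Sequence contrast of subject means, regimens pooled: (mP + mR + s + a)/2 − (mP + mR + s + b)/2 = (a − b)/2. Its null is a = b.
- Second minus first session, averaged over the two orders: s + (a + b)/2.
- Regimen averages over both sessions: P is mP + (s + b)/2 and R is mR + (s + a)/2.
- Sequence contrast within P only: (mP + s + b) − mP = s + b. Here sequence and session are the same indicator.

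With a = b = 6 and s = 0, the pooled sequence contrast is 0, the session contrast is 6, each regimen average moves by 3, and the within-P contrast is 6.

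**Simulation, assumed common shift of 6 units.** The documents give no carry-over size, so 6 is an assumption, as is a true BIS50 of 65. Settings: 16 steps per session; logistic model for unresponsiveness on BIS, regimen, their interaction and sequence; standard errors clustered by subject; test at 0.10; 1,500, 500 and 100 trials at the three sizes. The table shows the percentage of trials in which each term is flagged.

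| Situation | Term | N = 20 | N = 200 | N = 2000 |
|---|---|---|---|---|
| No shift | Sequence, pooled | 11.8 | 10.4 | 11 |
| Common shift | Sequence, pooled | 12.8 | 10.0 | 12 |
| Common shift | Session, pooled | 99.5 | 100 | 100 |
| Common shift | Sequence, within P | 58.5 | 100 | 100 |
| Common shift, regimens differ in slope and BIS distribution | Sequence, pooled | 10.8 | 17 | 70 |
| Shift in one regimen only | Sequence, pooled | 29.7 | 93.4 | 100 |

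At N = 20 the gap between 12.8% and 11.8% is within simulation error (standard error about √(0.12 × 0.88/1500) = 0.8 points for each figure). With the same curve in both regimens, BIS50 moved from 65.0 to about 62.0, that is 3/65 = 4.6%.

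A separate simulation at N = 20 gave 10.5% for the pooled sequence term (13% with no shift), 84.5% for the session term and 33.5% for the within-regimen fit (90% at N = 100).

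**Other shift sizes.** A third simulation used 20 subjects, 14 readings per session, a logistic slope of 0.2 per BIS unit and between-subject SD 7.5 or 15. A 9-unit common shift was flagged by the pooled sequence term in 10% to 11% of trials and by the session term in about 100%. A 4.5-unit shift was flagged in 10% against 70% to 72%.

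**Caution on the comparator.** With no shift, the session term was flagged in 14.7% of trials at N = 20 in the first simulation and 8% to 14% in the third. Its nominal 10% level is therefore somewhat exceeded with so few subjects, and its detection rates are slightly flattering.

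**Scale.** On the plan's CV, the standard error of BIS50 at n = 20 is 25%/√20 = 5.6%, or 3.6 units at a BIS50 of 65. A 3-unit displacement is about 0.8 of that, and lies inside the ±15% allowable error (9.75 units).

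**The case against.** The strongest reply is that SAP 7.3 does not commit to a pooled model. The documents analyse by regimen, and within a regimen the sequence indicator is the session indicator, so the test would respond to a common shift. This stands as a limit. It does not rescue the rule: the text permits two tests with different nulls, and the more favourable one still misses an assumed 6-unit shift in about 42% to 66% of trials at 20 subjects.

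A reader might infer that a common shift goes undetected at any sample size. The documents do not support that. Exact cancellation needs a pooled, additive, balanced model. When the regimens differ in slope and BIS distribution, the pooled term picks up the shift in 70% of trials at N = 2000. Subjects who complete one session are kept, which also disturbs the balance. At about 20 subjects none of this helps the pooled test.

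A reader might also infer that each regimen's BIS50 is biased. That is not supported either: no residual effect after the washout is documented, and every shift size above is assumed. Nor can the test be said to see only what remifentanil adds. The propofol steps match only nominally, because escalation ends on response, so propofol exposure can differ by regimen and only the common part cancels.

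Finally, a 2×2 design cannot separate common carry-over from a plain session effect, and a regimen-by-session term is the sequence term in another coding. Both points are right. What the fix adds is the session term, the reported size of the shift, and estimates free of any first-session influence.

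**Conclusion.** The concern holds in conditional form. Under a pooled fit, p ≥ 0.1 on the sequence term cannot support no carry-over. At about 20 subjects its result is practically the same with or without a common second-session shift, while each regimen's BIS50 would move by about half of that shift (about 3 units for an assumed 6). Under a within-regimen fit the test has the right target but detects the same shift only about 34% to 58% of the time. Even unequal carry-over, which the pooled term does address, is found in only 29.7% of trials when 6 units affect one regimen alone.

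These figures rest on assumed shift sizes, an assumed BIS50 of 65, roughly equal numbers in each order, and variability that the documents do not give. The defect lies in the decision rule and the unspecified model. Nothing in the documents shows that carry-over exists.

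**What to change.** In SAP 7.3:

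1. Specify one BIS-response model that allows for clustering within subject, with terms for regimen, session (first or second) and sequence (equivalently regimen-by-session). With about 20 subjects, use a small-sample correction.
2. Report the second-minus-first-session shift in BIS50 for each regimen with its 95% CI, and the average over regimens. The per-regimen shift compares different subjects and will be imprecise. If the plan's 25% CV is between-subject spread, 10 against 10 gives a standard error of 25% × √(1/10 + 1/10) = 11.2%. The average is a within-subject contrast.
3. Give first-session-only BIS50 (primary) and BIS95 (secondary) for each regimen as a sensitivity estimate.
4. Remove the rule that p ≥ 0.1 supports no carry-over, and state that the sequence term addresses only unequal carry-over.
5. Call the shift a second-session effect, since the design cannot attribute it to carry-over.

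The cost is SAP wording and one extra model. Visits 2 and 3 are already distinguished in the protocol's schedule, so no new data are needed. The first-session-only estimate has a wider interval. On the plan's CV the half-width goes from 1.96 × 25%/√20 = 11.0% to 1.96 × 25%/√10 = 15.5%, just beyond the ±15% allowable error, so it suits a sensitivity analysis rather than a replacement.

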14.3. Statistical Methods

Standard demographic information and baseline characteristics will be summarized using descriptive statistics. For safety assessments, adverse events (AEs) will be summarized using frequency counts and percentages. Descriptive statistics will be provided by severity and relationship as needed.

Any subject who responds to any verbal command with MOAA/S assessment score of 2, 3, 4, and 5 will be considered as responsive. Subjects with MOAA/S assessment scores of <2 will be considered unresponsive. Tetanic Electrical Stimulation (TES) will be employed with an MOAA/S assessment score of <2.

The BIS^{TM} index value collected from the left side of the brain will be used for primary analysis to reflect the typical operation of the device from this study. The BIS^{TM} index value collected from the right side of the brain will be used for internal research purposes.

The value of BIS^{TM} will be assessed at the different targeted-controlled drug concentrations or infusion rates. The logistic model (simplified Sigmoid E_{max} model) will be used to analyze the relationship between the BIS^{TM} index and loss of responsiveness through the probability of response curves. The values of BIS^{TM} , at which 50% (BIS_{50}) and 95% (BIS_{95}) of subjects are unresponsive, and their 95% confidential intervals will

be derived. The systematic variance between groups will be evaluated. The Prediction Probability score (P_k) for correctly predicting if the subject was responsive or unresponsive will be assessed.

15. Ethics

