## 6 Determination of Sample Size

---

Up to 30 subjects will be enrolled to collect data from approximately 20 subjects and to account for anticipated screen failures and subject dropouts. Based on the dose-response Hill equation (extended logistic regression) with an allowable error of  $\pm 15\%$  for BIS50 and coefficient of variation of 25% at the alpha level of 0.05, the sample size will provide adequate power (>80%) to evaluate the performance of anesthetic agents/regimens.

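### SAP 7.3 treats a non-significant sequence term, in about 20 sequentially assigned subjects, as support for no carry-over, with no margin, confidence interval or clustering specified

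*SAP*

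**What the plan says.** The method in SAP 7.3 is one sentence: "Logistic regression will be used to test carry-over effect by using the regiment sequence as an indicator variable". The decision rule is: "A P-value of 0.1 or larger will be deemed as supporting the assumption of no carry-over effect". If the test goes the other way, the plan is open-ended: "If the carry-over effect is present, further analysis will be performed by adopting appropriate statistical methods", with one published crossover method cited as an example. Protocol section 14 does not mention carry-over.

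The design facts that bear on this are:

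- **Size.** SAP 6: "Up to 30 subjects will be enrolled to collect data from approximately 20 subjects".
- **Allocation.** Protocol 6 and SAP 5 describe a non-randomised cross-over in which subjects are assigned sequentially to a starting regimen, with a washout of at least 1 week.
- **Repeated scoring.** Each subject has two procedure visits. At each, SAP 5.1 says, the "MOAA/S score will be assessed when the patient is awake and at the different targeted concentrations". The plan lists eight propofol targets, stepped up and then down.
- **What is reported.** SAP 7.9: "The estimated BIS values along with 95% confidence intervals will be provided for propofol with or without remifentanyl regimens". Protocol 14.3 likewise derives BIS50 and BIS95 with 95% intervals.

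**The concern.** There are two separate faults.

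The first is logical and needs no arithmetic. The rule converts failure to reject into positive support. That is defensible only with a margin for negligible carry-over and an interval or power to set against it, and neither document has any of these. A threshold of 0.10 instead of 0.05 flags somewhat more readily, but does not change what a non-significant result means.

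The second is that the test is weak and under-specified. Sequence is constant within a subject, so the contrast is between two small groups. Because the groups are not randomised, a sequence difference can reflect who was in them, and such a difference can also mask carry-over. The logistic model names no subject effect, no clustered errors and no period term, although each subject contributes many scores.

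At stake is what the report may say. A pass could be presented as evidence for an assumption the data can hardly test. A failure, possibly spurious, would lead to an analysis chosen after seeing the data.

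**Working it through.** **1. The plan's own power figure.** SAP 6 and Protocol 14.1 give an allowable error of 15% for BIS50, about 20 subjects, power above 80%, and a "coefficient of variation of 25% at the alpha level of 0.05". As a one-sample mean, d = 0.15/0.25 = 0.6 and power ≈ Φ(0.6 × √20 − z). One-sided: Φ(2.683 − 1.645) = 85.0%. Two-sided: Φ(2.683 − 1.960) = 76.5%. The stated figure therefore reproduces on a one-sided reading; the plan does not state sidedness. It concerns BIS50, not carry-over. No power is given for the test in SAP 7.3.

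**2. Illustration of a valid sequence test.** This is not the SAP's logistic test.

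From the documents:
- about 20 subjects and the 0.10 threshold;
- CV 25%, read here as the SD of BIS50 in one period (relative scale, mean 1);
- 15%, borrowed from the allowable error because no carry-over size is given.

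Assumed:
- a BIS50 can be attached to each subject and period;
- 10 subjects per sequence, two-sided test;
- between-period correlation ρ from 0 to 0.8;
- the shift occurs at the second visit of one sequence only. An equal shift in both sequences would look like a period effect, and the sequence contrast on the total would not see it.

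Formulas:
- two-period total: SD = 0.25 × √(2 + 2ρ);
- per-regimen contrast (one sequence at its first visit, the other at its second): SD = 0.25, no ρ needed;
- SE = SD × √(1/10 + 1/10); non-centrality = shift/SE;
- non-central t, 18 df, critical value 1.734;
- largest observed difference that still gives p ≥ 0.1 = 1.734 × SE.

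| Contrast | SD | SE | Non-centrality, 15% shift | Power, 15% | Power, 30% | Largest difference that passes |
|---|---|---|---|---|---|---|
| Total, ρ = 0 | 0.354 | 0.158 | 0.949 | 23.7% | 57.2% | 27% of BIS50 |
| Total, ρ = 0.5 | 0.433 | 0.194 | 0.775 | 19.3% | 44.0% | 34% |
| Total, ρ = 0.8 | 0.474 | 0.212 | 0.707 | 17.8% | 39.0% | 37% |
| Per regimen | 0.25 | 0.112 | 1.342 | 36.3% | 82.5% | 19% |

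With a 12/8 split, power for a 15% shift is 17-23% on the total and 35% per regimen. With 15 per sequence (all 30 completing) it is 22-31% and 48%.

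Put in terms of the rule: with no carry-over a valid test passes 90% of the time. With a 15% second-visit shift it still passes 76-82% of the time on the total (1 − 0.237 to 1 − 0.178), or 64% per regimen (1 − 0.363). A pass hardly separates the two cases.

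**3. What happens if clustering is ignored.** A rough simulation used 20 subjects, 14 assessments per visit, 600 runs per setting, and an assumed slope and variances. The logistic model contained BIS, regimen and sequence.

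| Fit, nominal 0.10 | Rejects, no carry-over | Rejects, 15% second-visit shift |
|---|---|---|
| Assessments as independent | 43-54% | 62-66% |
| Errors clustered by subject | about 11% | 19-27% |

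A second rough simulation with its own assumed variances gave about 60% and 14% with no carry-over. The exact rates depend on those assumptions; the direction does not differ between the two. With clustered errors, the rejection rate under a 15% shift is close to the 18-24% in step 2.

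**The case against.** The strongest case on the other side has four parts.

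- **Little hangs on the rule.** BIS50 and BIS95 are estimated per regimen with intervals, no formal test between regimens is defined, and nothing makes the estimates conditional on SAP 7.3. This stands and sets the severity. A reader might infer that the primary result passes through a two-stage procedure steered by the pre-test; the documents do not say so.
- **The washout already makes the argument.** With at least 1 week between regimens, carry-over may well be negligible. This also stands: nothing here shows that carry-over is likely. It is a reason to rest the assumption on the washout rather than on a p-value.
- **The power figures are not the SAP's.** The 15% and the 25% belong to the sample-size statement, and the SAP treats BIS50 as a population value from a fitted curve, not one value per subject. This stands, so the figures are illustrative only. It also limits them: a 39-57% band might be read as power for a 15% carry-over defined on the subject's mean. Carry-over cannot act at the first visit, so that band is a 30% second-visit shift on the two-period total. In a per-regimen contrast, the same 30% shift would be detected with about 83% power.
- **The rule may not be lenient.** If the model is fitted without clustering, the main error is false alarms. This stands too. A reader might infer that the test as written always passes too easily; the SAP does not specify the model well enough to say so.

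None of this answers the logical point: with no margin and no interval, p ≥ 0.1 does not support absence.

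**Conclusion.** The concern holds as a minor one. The rule in SAP 7.3 is unsound as written, because it takes non-significance of a between-subject, non-randomised factor in about 20 subjects as support for no carry-over. That conclusion rests on the text alone, and confidence in it is high.

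The size is less certain. Under the stated assumptions, power for a 15% second-visit shift is about 18-24% on the two-period total or about 36% per regimen. Observed differences of up to 27-37% of BIS50 (total) or 19% (per regimen) would pass. If assessments are treated as independent, the fault reverses and false alarms dominate. The SAP leaves open which of these applies.

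The documents do not support reading this as bias in the per-regimen BIS50 or BIS95, or as evidence that the washout is inadequate.

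**What to change.** In SAP 7.3:

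1. Delete the p ≥ 0.1 rule.
2. Report the sequence estimate with a confidence interval, as descriptive, from a model with period and regimen terms and either subject-clustered errors (small-sample corrected) or a subject random effect. The wording should go no further than *no carry-over detected*.
3. State that sequence is not randomised and that the no-carry-over assumption rests on the washout of at least 1 week.
4. Keep the all-data per-regimen BIS50 and BIS95 as primary. Pre-specify first-period-only BIS50 and BIS95 as a sensitivity analysis, in place of the unspecified further methods. This keeps a defined response to a sequence signal, which simply declaring the main estimates final would lose.

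Cost: SAP wording and one extra set of estimates, with no added subjects and no design change. There would be no formal carry-over test to cite. The first-period result would also be less precise: with about 10 instead of 20 subjects per regimen, and if precision scales with the number of subjects, its intervals would be about √(20/10) = 1.4 times as wide. Any comparison of regimens in that analysis would be between non-randomised groups.
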